	
only).
 
Details of any other populations for analysis will be described in the statistical analysis plan (SAP).
 
Statistical Analysis
 
Assumption of sample size calculation:
 
• Study design: Simon's optimal two stage design^{1,2}• Type I error (one-sided): 10%• Power: 80%• Response probability of null hypothesis (P0): 0.10• Response probability of SCB01A (P1): 0.25 
According to these hypotheses, up to 64 patients need to be recruited into the study (including patients from the run-in phase). At least 6 patients are required to achieve CR, PR or SD at the end of the 9th week after first treatment with SCB01A for the study to meet its primary objective. The trial will be discontinued if DC is observed in one or none patients after the Stage 1 Disease Controls Review.
 
Stopping rule: stopped early for futility if less than 2/13 (including 0 or 1 of 13 patients) show DCR in Stage 1 of Phase II with no further investigation of the drug if less than 6/34 achieve DCR by the end of Stage 2 of Phase II.
 
Both according to FAS and PP approaches (all enrolled patients who meet the eligibility criteria and do not present major deviations during the study) will be included in the analyses. The conclusion will be summarized according to analyses of PP population. Inferential analysis results will be expressed as point estimates and their 95% confidence intervals (CIs). To be consistent with the sample size calculation, the 90% CI will also be presented. Analyses will be carried out using SAS® Software, version 9.3 or higher (SAS Institute, Cary, North Carolina, USA).
 
All time-to-event endpoints, including OS time and PFS, will be reported in days (median with 95% CI and range) and calculated using Kaplan-Meier methods. Patients who have not progressed or who have died at the time of the analysis will be censored at the last disease assessment date.
 
PK Evaluations
 
The blood samples will be assayed for SCB01A and PK parameters (area under the plasma concentration-time curve from time zero to time t [AUC_{0-t}], area under the plasma concentration-time curve from time zero to infinite time [$AUC_{0-\infty}$], and maximum plasma concentration [C_{max}], clearance [CL], volume of distribution [V_d], half-life [$t_{1/2}$], elimination

--	--

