	
constant $[K_{el}]$, mean residence time [MRT] and time to maximum concentration $[T_{max}]$) will be determined and presented graphically and descriptively (as appropriate).
 
A detailed SAP will be finalized prior to final database lock. Any significant changes to the analyses described in this protocol will be highlighted in the SAP and the Clinical Study Report.

Duration of the Study	The planned duration of the entire study is approximately 30 months with an enrolment period of 12 months.
End of Study	The study will be completed 36 weeks after the last patient receiving 1 st treatment with SCB01A

Table 1: Study Schedule, Run-in phase (Dose 1, 0a, 1a, 2, 2a, 3, 3a, and 4 SCB01A)

Study Visit ¹	Screening	C1D1	C1D8	C1D15	C2D1	C2D8	C2D15	C3D1	C3D8	C3D15	C4D1-CXD1 ⁴	C4D8-CXD8 ⁴	EOT/Early Withdrawal ²	Follow-Up (Phone Call) ³	Un-scheduled
Study Days	-28 to -1	1 (± 0)	8 (± 1)	15 (± 2)	22 (± 1)	29 (± 1)	36 (± 2)	43 (± 1)	50 (± 1)	57 (± 2)	64 (± 1)	71 (± 1)	NA	NA	NA
Activities															
Informed Consent	X														
Medical History	X														
Eligibility Criteria	X	X													
Physical Examination	X	X	X	X	X	X	X	X	X	X	X	X			X
Vital Signs	X	X	X	X	X	X	X	X	X	X	X	X			X
BSA Calculation		X	X		X	X		X	X		X	X			
ECOG Performance Status	X	X	X	X	X	X	X	X	X	X	X	X			X
Adverse Events Review ⁵	X	X	X	X	X	X	X	X	X	X	X	X		X	X
Concomitant Medication Review	X	X	X	X	X	X	X	X	X	X	X	X		X	X
12-Lead ECG ⁶	X	X	X		X	X		X	X		X	X			X ¹⁶
Radiological Image Assessments ⁷	X										X			X	X ¹⁶
Safety Laboratory	X	X ⁸	X	X	X	X	X	X	X	X	X	X			X ¹⁶
Urinalysis	X	X ⁸			X			X			X			X	X ¹⁶
Serum Pregnancy Test ⁹	X														
Coagulation		X ⁸	X	X	X	X	X	X	X	X	X	X			X ¹⁶
HPV	X														
Study Drug Administration		X	X		X	X		X	X		X	X			
EORTC Questionnaires ¹⁰	X		X	X	X	X	X	X	X	X	X	X			
PK ¹¹		X	X		X	X		X	X						
Biomarker ¹²		X								X					

Study Visit ¹	Screening	C1D1	C1D8	C1D15	C2D1	C2D8	C2D15	C3D1	C3D8	C3D15	C4D1-CXD1 ⁴	C4D8-CXD8 ⁴	EOT/Early Withdrawal ²	Follow-Up (Phone Call) ³	Un-scheduled
Study Days	- 28 to -1	1 (± 0)	8 (± 1)	15 (± 2)	22 (± 1)	29 (± 1)	36 (± 2)	43 (± 1)	50 (± 1)	57 (± 2)	64 (± 1)	71 (± 1)	NA	NA	NA
Activities															
DCE-MRI ¹³	X	X													
Survival Status ¹⁴														X	
Cancer Therapy ¹⁵														X	
Nerve Conduction Velocity ¹⁷	X														

¹ Patients may continue treatment beyond 3 cycles (9 weeks) of SCB01A treatment per investigator discretion if they are experiencing clinical benefit, until the study is terminated.

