4.10. Blinding

This is an open-labelled study. Therefore blinding procedures are not applicable.

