8.1. Statistical and Analytical Plans

A brief description is given of the planned analysis methodology. Detailed descriptions of the statistical analysis methods and data conventions will be provided as a separate document; i.e., the Statistical Analysis Plan (SAP). The SAP may also include additional exploratory analyses not explicitly mentioned in the following sections. A detailed SAP will be finalized prior to final databased lock. Any significant changes to the analyses described in this protocol will be highlighted in the SAP and the Clinical Study Report.

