8.8. Interim Analysis

An interim statistical analysis will be performed following the completion of stage 1, Phase II. If more than two DCs are observed, an additional 21 patients will be enrolled into Stage 2 at the same dose level. The study will be stopped early for futility if less than 3 DCRs are observed following the completion of the first stage of Phase II with no further investigation of the drug if less than 6/34 achieve DCR by the end of Stage 2 of Phase II.

9. Study Management

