Continuous variables will be reported to the same precision as the source data. Derived variables will be reported using the same precision to the value(s) from which they were derived. For the reporting of descriptive statistics, the mean (95% CI) and median will be reported to 1 decimal place more than the source data; the minimum, and the maximum values will be presented to the same precision as the source data; and standard deviation will be reported to 2 decimal places more than the source data. Rounding is not allowed in the middle of the calculation. It only takes place at the last step to report the final result. Post-dose time points/visits will be calculated relative to start time of infusion on Day 1. Study day will be defined as assessment day minus dosing day +1.

Analysis will be conducted for run-in phase I only. The dose levels (cohorts) will be referred to in the text, tables and listings as follows,

- 3.25 mg/m² (Dose 1)
- 12 mg/m² (Dose 2)
- Total

4. Analysis Populations

The protocol pre-specified the analysis populations of Full Analysis Set, Per-protocol, Safety and PK. However, this study was terminated early with only five (5) subjects enrolled, thus the analysis populations were modified accordingly as follows.

Furthermore, any additional analysis populations not identified in the SAP will be identified in the final CSR as post hoc analyses. This may include the addition of additional study populations or subgroups of interest.

- **Full Analysis Set (FAS):** The FAS consists of all subjects enrolled in the run-in phase. This population will be used for the listing and summary of efficacy, health outcome, and bioanalytical measurement data.
- **Safety population:** The safety population will consist of all subjects who received at least one dose of SCB01A. All safety, treatment exposure, demographic and baseline characteristic data will be listed and summarized using the Safety Population
- **PK population:** The PK population will consist of all subjects who received at least one dose of SCB01A with sufficient post-dose bio-samples collected for PK profile characterization. PK analysis will be conducted using the PK Population.

5. Subject Disposition

All subjects who provide informed consent and are enrolled will be accounted for in this study. Subject disposition will be summarized using the Safety Population.

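### The SAP is due only before final database lock, not before the Stage 1 interim, while the Stage 1 cut-off, DCR denominator, missing Week 9 scans and timing of per-protocol exclusions remain unsettled

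*Protocol*

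**What the plan says.** The Synopsis (Statistical Methods) states "A detailed SAP will be finalized prior to final database lock", and section 8.1 repeats it: "A detailed SAP will be finalized prior to final databased lock". Both places add that "Any significant changes to the analyses described in this protocol will be highlighted in the SAP and the Clinical Study Report".

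Section 8.8 plans a formal look: "An interim statistical analysis will be performed following the completion of stage 1, Phase II". That look decides whether 21 more patients enter Stage 2. Section 4.10 says "This is an open-labelled study", and section 3.1 describes a single arm.

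The protocol itself fixes a good deal:
- DCR is CR, PR or SD at Week 9 by RECIST 1.1 (Synopsis, Endpoints).
- The FAS and PP sets are defined (Synopsis; section 8.3), and the PP set carries the conclusion (Synopsis, Statistical Analysis).
- The null and target rates, error rate, power and final requirement of at least 6 of 34 are given (Synopsis; sections 8.2 and 8.8).

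The SAP is left the detailed methods and data conventions (section 8.1) and additional sets: "Details of any other populations for analysis will be described in the statistical analysis plan (SAP").

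The SAP that exists was written after the trial stopped in the run-in with five patients enrolled (SAP section 1). In SAP section 4 it says of the protocol's sets: "thus the analysis populations were modified accordingly as follows". SAP section 10.1 pools the Week 9 evaluation with the end-of-treatment or early-termination evaluation and uses the result as best overall response up to Week 9.

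**The concern.** With no blinding and no control arm, each response is visible as it occurs. The only protection for the error rate is that the counting rules are fixed before the counts are known. The stated deadline does not give that protection at either decision. Stage 1 may be decided before any SAP exists. The last Week 9 result is also available about 27 weeks before the study ends, because the end is 36 weeks after the last patient's first dose (36 − 9 = 27).

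This would matter little if the protocol were complete and consistent on the primary endpoint, but it is not. The cut-off at which Stage 1 stops, the patients in the denominator, the status of a patient with no Week 9 scan, and the date on which the Medical Monitor's PP exclusions are made all affect the go/no-go result or the estimate. Each is either stated in conflicting ways or not stated.

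**Working it through.** **1. Reproduce the stated design.** Inputs (Synopsis, Statistical Analysis): P0 = 0.10, P1 = 0.25, one-sided α = 0.10, power 0.80, Simon optimal design, stop at 0 or 1 of 13, success at 6 or more of 34.

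With X1 ~ Bin(13, p) and X2 ~ Bin(21, p),

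P(success) = Σ over x ≥ 2 of P(X1 = x) × P(X2 ≥ 6 − x).

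| x | P(X1 = x), p = 0.10 | P(X2 ≥ 6 − x) | Product | Product, p = 0.25 |
|---|---|---|---|---|
| 2 | 0.2448 | 0.1520 | 0.0372 | 0.1664 |
| 3 | 0.0997 | 0.3516 | 0.0351 | 0.2329 |
| 4 | 0.0277 | 0.6353 | 0.0176 | 0.2057 |
| 5 | 0.0055 | 0.8906 | 0.0049 | 0.1255 |
| ≥ 6 | 0.0009 | 1 | 0.0009 | 0.0802 |
| Sum | | | **0.0957** | **0.8108** |

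A search over two-stage designs with up to 45 patients, meeting α ≤ 0.10 and power ≥ 0.80, returns exactly 1/13 and 5/34 as the optimal design (expected N 20.95 under P0). The stated figures therefore reproduce with the Synopsis rule.

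**2. Stage 1 cut-off.** The texts disagree:
- Stop at 0 or 1: Synopsis, and SAP section 2.1.
- Stop at 2 or fewer: section 8.2 directly; section 3.1 (continue if more than two); sections 8.5 and 8.8 (stop if fewer than three).

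Under the second reading the x = 2 row drops out:
- type I error = 0.0957 − 0.0372 = 0.0585
- power = 0.8108 − 0.1664 = 0.6444
- probability of stopping early under P0 rises from 0.621 to 0.866.

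The stated 80% power is lost.

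**3. Denominator.** Four descriptions coexist:
- FAS and PP are both analysed, with PP carrying the conclusion (Synopsis).
- Evaluable patients have a baseline assessment within 4 weeks of starting treatment and at least one on-study assessment (Synopsis; section 8.5).
- PP requires at least three completed cycles and a post-baseline RECIST assessment (section 8.3).
- The Stage 1 committee review uses patients who completed three cycles (section 3.1).

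If the fixed count of 6 is kept and no one is replaced, removing patients without disease control does not change the decision. It matters if the smaller set is re-tested. As an illustration, with the number excluded assumed, 5 of 34 fails the rule. If 10 patients without disease control leave, 5 of 24 gives a naive exact one-sided p = P(Bin(24, 0.10) ≥ 5) = 0.085. With 9 leaving, 5 of 25 gives 0.098. With 8 leaving, 5 of 26 gives 0.112.

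**4. Letting 5 count as success.** Keep the 1/13 gate and lower the final requirement to 5. At p = 0.10 this is Σ over x ≥ 2 of P(X1 = x) × P(X2 ≥ 5 − x) = 0.1805, against 0.0957. This is an upper bound for a choice that rescues every trial with exactly 5.

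**5. Missing Week 9 scans and PP exclusions.** The protocol gives no rule for a patient without a Week 9 scan. PP exclusions for major deviations or adverse events rest on the Medical Monitor's judgement, with no date and no requirement that they precede sight of responses.

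**6. What the existing SAP did.** Compared with the protocol:
- FAS: the condition of three cycles or a DLT for run-in patients is gone.
- PP: no longer listed; efficacy moves to the FAS (SAP section 10).
- Safety: the condition of a post-dose safety evaluation is gone.
- Response: pooled as described above, so stable disease at an early-termination visit could count as disease control, although SAP section 2.3 still defines DCR at Week 9.

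SAP section 4 discloses the population changes and gives early termination as the reason. SAP section 10.1 does not flag the pooled rule as a change, and SAP section 15 covers only later departures from the SAP itself.

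**The case against.** A SAP finalised before lock is common and is not an error in itself. The protocol already contains the endpoint, the sets, the set for the conclusion and the final cut-off. The sentence after the deadline requires significant changes to be highlighted, section 9.10.2 requires other analysis changes to be described in the study report, and the SAP says that unplanned analyses and added sets will be identified as post hoc. An earlier date would not by itself cure contradictory text.

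Most of this stands. A reader might infer that all DCR rules and analysis sets are open until lock; the protocol's own definitions rule that out. Disclosure of changes does not cover the gaps, however. Choosing between two cut-offs that both stand in the protocol, or adding a rule for missing scans, need not be recognised as a change. The earlier date helps only if the four items are settled in the document, so the two belong together.

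A reader might also infer that the SAP's rules were chosen with the five patients' responses in view. No document shows who had seen those responses when the SAP was written. Widening the FAS to all enrolled run-in patients and dropping PP is the less selective direction. The restricted list of outputs is attributed to limited data.

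Nor should the size be overstated. If the counted rate were 15% when the true rate is 10%, the design would pass with probability 0.338. That 15% is an assumption with no basis in the documents, and it is applied in both stages. The same wider rule written before the first patient would give the same figure, so it does not measure the effect of late timing.

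**Conclusion.** The point holds in limited form. The SAP deadline is not tied to the Stage 1 interim in an open-label, single-arm trial, and four items bearing on the primary decision are left contradictory or open until final lock. The cut-off conflict alone moves power from 0.81 to 0.64. A post hoc choice that let 5 of 34 count as success would move type I error from 0.096 to at most 0.18. These figures assume independent binomial outcomes, 13 and 21 patients, and the stated P0 and P1.

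The consequence is for the design as written. No Phase II patient was enrolled and no interim took place (SAP sections 1 and 16.1), and the five-patient efficacy analysis is descriptive, so no error rate was spent. For the existing SAP, what remains is one of labelling: the pooled response rule departs from DCR at Week 9 and is not marked as a departure.

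**What to change.** In the Synopsis and section 8.1, replace the deadline sentence with: *The SAP will be finalised before the first Phase II patient is dosed and in any case before the Stage 1 interim analysis; later changes will be dated, justified and reported as post hoc.*

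Settle four items in that SAP and align the protocol with them:
1. One Stage 1 cut-off in the Synopsis and in sections 3.1, 8.2, 8.5 and 8.8. Of the two readings, only stopping at 0 or 1 of 13 reproduces the stated power.
2. One denominator for the DCR decision, with the count required if it can differ from 34.
3. The status of patients with no Week 9 scan.
4. A date for PP exclusions that precedes review of responses.

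In the existing SAP, state in sections 4 and 10.1 that the population changes and the pooled Week 9/end-of-treatment rule are departures from the protocol made after early termination of an open-label trial. Do not assert that responses had been reviewed.

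The cost is earlier drafting and less later flexibility. No patients, visits or analyses are added, and the 13/34 design is unchanged.

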1.1. Background

Vascular disrupting agents (VDAs) are designed to disrupt the already abnormal vasculature that supports tumors by targeting their already dysmorphic endothelial cells. VDAs induce rapid and selective shutdown of the tumor blood supply resulting in tumor death while leaving the blood supply in normal tissues relatively intact^{3,4}. The largest group of VDAs is the tubulin-binding combretastatins. Combretastatin A4 phosphate (CA4P) is a small organic molecule found in the bark of the African bush willow tree (*Combretum caffrum*)³. Endothelial cells have been shown to be particularly sensitive to the effects of CA4P compared with various other cell types and several preclinical studies have demonstrated selective *in vitro* activity of CA4P against proliferating endothelial cells³.

SCB01A is a novel heterocyclic combretastatin A-4 (CA-4) analogue that binds to the colchicines-binding site of the β-subunit of tubulin thereby inhibiting polymerization and effectively preventing mitosis in a manner similar to that seen with other “spindle poisons”, e.g., vincristine, vinblastine and vinorelbine, which are in use as cancer chemotherapeutic agents. Because SCB01A has VDAs property, SynCore plans to develop SCB01A as a treatment for a variety of oncologic indications such as non-small cell lung cancer, breast cancer, head and neck cancer, acute lymphoblastic leukemia, nephroblastoma and testicular cancer.

Compounds that interfere with the cell cycle by interfering with normal biology of tubulin are prominent anti-cancer agents because they can inhibit the proliferation of tumor cell lines derived from various organs. Tubulin-containing structures are important for diverse cellular functions, including chromosome segregation during cell division, intracellular transport, development and maintenance of cell shape, cell motility, and possibly distribution of molecules on cell membranes. The drugs that interact with tubulin are heterogeneous in chemical structure. However, a common characteristic of these agents is that while binding to tubulin, they cause its precipitation and sequestration to interrupt many important biologic functions that depend on the microtubular class of subcellular organelles. One class of well-characterized and clinically used antimitotic drugs is those of natural origin, including the taxanes (paclitaxel, docetaxel), vinca alkaloids (vincristine, vinblastine, vinorelbine) and podophyllotoxins. These agents either inhibit the polymerization of tubulin (vinca alkaloids) or prevent the disassembly of microtubules (taxanes).

SCB01A has been studied extensively since 2005 to evaluate its pharmacokinetic (PK) profile, metabolism, *in vitro* genotoxicity and acute and sub-acute toxicity. SCB01A binds to colchicine binding sites of tubulin much more strongly than colchicines, and as with other antimicrotubule inhibitors, it arrests the cells on the G2/M phase in a time- and concentration-dependent manner, subsequently leading to cell apoptosis. Additional studies indicate that the effect of SCB01A on cell-cycle arrest is associated with an increase in cyclin B1 levels and a mobility shift of Cdc2 and Cdc25C. The changes in Cdc2 and Cdc25C coincide with the appearance of phosphoepitopes recognized by a marker of mitosis, MPM-2. Furthermore, phosphorylated forms of

Bcl-2, perturbed membrane mitochondrial potential, and activation of the caspase 3 cascade may be involved in SCB01A-induced apoptosis.

Two phase I clinical studies were performed “A Phase 1 Dose Escalation Study of SCB01A in Subjects with Advanced Solid Tumors Who Have Failed Standard Therapy” and “Long-Term Compassionate Use Study for Continued Administration of SCB01A in Subjects Who Completed Treatment With SCB01A in the Previous Protocol #SCB01A-01” respectively. The phase I study demonstrated that SCB01A has encouraging safety and efficacy and support for further Phase II study. 33 subjects were enrolled in the study and 31 subjects completed the main treatment. Among the 31 subjects, 11 of them completed the extension treatment of SCB01A. Up to date, 5 subjects, two in main and extension period respectively, experienced 7 SUSAR events. (Including gastric ulcer bleeding, thrombocytopenia, cough, radiation recall dermatitis and thromboembolic event, Muscle weakness lower limb and Sepsis). In addition, 5 dose limiting toxicities and 61 adverse reactions were reported in this study.

The aim of this Phase II study with SCB01A is to determine the effect of SCB01A in patients with squamous cell carcinoma of head and neck who have failed previous platinum based therapies.

2. Study Objectives

2.1. Run-In Phase:

Primary Objective

To determine the optimal dose for 3 cycles of i.v. administration of SCB01A on Days 1 and 8 of each cycle in a 3-week cycle.

Secondary Objective:

To evaluate the safety and toxicity for 3 cycles of i.v. administration of SCB01A on Days 1 and 8 of each cycle in a 3-week cycle

2.2. Phase II:

Primary Objective:

To assess the disease control rate (DCR) at the end of the 9th week (3 cycles, each cycle consists of 21 days) after treatment with SCB01A, according to the Response Evaluation Criteria in Solid Tumors (RECIST) version 1.1.

Secondary Objectives

The secondary objectives of the study are listed below:

- To assess the overall survival rate at 36 weeks after treatment of SCB01A in patients with recurrent or metastatic squamous cell head and neck cancer who have previously been treated with platinum therapy.
- To assess the progression-free survival (PFS)
- To determine the recommended dose regimen of SCB01A for further investigation in different settings of head and neck squamous cell cancer.
- To assess the safety and toxicity profile of study treatment.
- To assess the PK profile of SCB01A of patients in the run-in phase.
- To assess health outcomes using patient-reported European Organization for Research and Treatment of Cancer Quality of Life Questionnaires (EORTC QLQ-C30) and EORTC QLQ H&N35 questionnaires.
- To assess biomarkers relevant to the efficacy and mechanism of action of SCB01A.
- To explore the possible association between biomarkers and clinical outcomes.

3. Investigational Plan

